TAP Block Study

NCT05537883

IRB Approval Date: 07AUG2023

Study Title: Single Blinded Randomized Trial of Transversus Abdominis Plane Block Using Liposomal Bupivacaine in Metabolic and Bariatric Surgery Patients

Principal Investigator: [name]

Co-Investigators: [name], [name]

Sponsor or funding source: Wake Forest University Health Sciences

Background, Rationale, and Context

The transversus abdominis plane (TAP) block was described in 2007 using an ultrasound to inject local anesthetic between the internal oblique and transversus abdominis muscles where the sensory nerves of the abdominal wall travel [1]. The TAP block can also be performed by the surgeon with laparoscopic guidance. TAP block has been shown to provide analgesia after abdominal surgery, decreasing opioid use, and is widely accepted into practice [2]. TAP block has become a cornerstone in enhanced recovery after surgery programs, as well as part of multimodal analgesia, and opioid reducing efforts nationwide. A recent meta-analysis of Randomized Controlled Trials (RCT) comparing TAP block with bupivacaine or ropivacaine to no TAP block in bariatric surgery showed reduced postoperative nausea and vomiting and time to ambulation [3]. Liposomal bupivacaine compared to plain bupivacaine has been touted to provide a longer duration of analgesia (up to 72 hours) by slowly releasing the anesthetic agent into local tissue. A recent systematic review comparing liposomal bupivacaine to conventional local anesthetic agents in regional anesthesia, including TAP blocks, showed conflicting results so no definitive conclusions could be made [4]. It is unclear if liposomal bupivacaine is superior to plain bupivacaine for TAP blocks in bariatric surgery. Our study would be the first RCT comparing laparoscopic TAP block with liposomal bupivacaine vs plain bupivacaine in a bariatric surgery population.

Objectives

Compared to only Bupivacaine administered via TAP block, we will investigate the analgesia effects to patients undergoing metabolic and bariatric surgery receiving TAP block with a Liposomal Bupivacaine mixture.

Primary Objective: To determine if patients undergoing metabolic and bariatric surgery receiving TAP block with a Liposomal Bupivacaine results in pain scores, as measured by visual analogic scale (VAS), that are equivalent compared to patients receiving TAP block with Bupivacaine only.

Primary Hypothesis:

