- 1) Lower values of the outcome variable VAS are desirable, and the hypothesis is listed below –

Hypothesis 1. 1

$H_0: \mu_E - \mu_S \geq \delta$ (Study group is different compared to the active control group by δ or more)

$H_1: \mu_E - \mu_S < \delta$ (Study group is equivalent to the active control when difference is within prespecified δ)

Where μ_E, μ_S are the population means for the outcome VAS measured at 24 hours after surgery for the study group (E) and the standard (S) active group, respectively

δ is non-inferiority margin, specified in advance based on clinical judgement. Based on our clinical experience, $\delta = 1.5$

Secondary Objectives: Compared to TAP block with Bupivacaine only, we will compare opioid consumption, and other effect differences to patients undergoing metabolic and bariatric surgery receiving TAP block with Liposomal Bupivacaine.

Secondary Hypotheses

Hypothesis 2.1 – Patients undergoing metabolic and bariatric surgery receiving TAP block with Liposomal Bupivacaine results in less opioid consumption before hospital discharge /during the first 48 hours postoperatively as measured in morphine equivalents (mg) compared to patients receiving simply TAP block with Bupivacaine only.

Hypothesis 2.2 - Patients undergoing metabolic and bariatric surgery receiving TAP block with Liposomal Bupivacaine results in pain score as measured by visual analog scale (VAS) at 12 hours after surgery that are equivalent compared to patients receiving TAP block with Bupivacaine only.

Exploratory objectives: We will explore other effects, including pain score at 48 hours, and 72 hours after surgery, total opioid consumption required post op during their one-week post op visit as measured in morphine equivalences.

Methods and Measures

Design

This study is a 2-arm parallel single blinded randomized equivalency, single-center, clinical trial. Patients will be blinded to type of TAP block used.

Setting

This study will take place at Atrium Health, an academic medical center.

Subjects selection criteria

Inclusion Criteria

To be eligible for enrollment in this study, participants must meet all the following criteria:

1. Adult, age > 18 years
2. Participants who can give written informed consent and willing to comply with all stud-related procedures.
3. Patients undergoing primary sleeve gastrectomy or roux-en-y gastric bypass

Exclusion Criteria

1. Patients undergoing duodenal switch procedures

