2. Patients undergoing concomitant hiatal hernia repair or ventral hernia repair or cholecystectomy at time of primary metabolic surgery
3. Patients with chronic opioid use

Sample Size

The number of patients required in each group is determined from a power analysis based on primary hypothesis.

In this study, based on our clinical experience, we assume standard deviation for each group is 3, the margin of equivalence is 1.5 on NRS, and the true difference between the two groups is 0 on the NRS. Group sample size of 88 from each group achieves 90% power to detect our prespecified equivalence margins, with alpha of 0.05. Assuming a 20% dropout or withdrawal based upon previous experience, 106 subjects per group will be required.

Interventions and Interactions

There will be two groups: (1) active control and (2) study group. Active control group patients receive TAP block with a Bupivacaine only mixture, containing 50 mL 0.5% Bupivacaine, and 100 mL normal saline solution. Study group patients will receive TAP block with a Liposomal Bupivacaine mixture, containing 20 mL Liposomal Bupivacaine, 30 mL 0.5% Bupivacaine, and 100 mL normal saline solution. TAP block technique will be standardized using subcostal as well as anterior axillary line as landmarks, injecting down to level of T10, using laparoscopic-guided approach. TAP block will be administered at the start of every case, after the first port is placed upon laparoscopy. Type of anesthesia administered will also be standardized including the use of narcotics, lidocaine, inhalational anesthesia and Ketamine.

Randomization schedules will be generated by SAS 9.4 (SAS Institute Inc., Cary, NC) by using a masked block randomization procedure. Eligible patients will be randomized with a 1:1 ratio between the 2 groups of patients receiving TAP block Exparel mixture or simply bupivacaine administered via TAP block. Research Electronic Data Capture (REDCap) randomization

module will be used to manage randomization and allocate treatment groups. The allocation sequence will be concealed with application of the REDCap.

Outcome Measure(s)

Primary Outcome measures

1. Pain score at 24 hours post-operative, using visual analogue scale (VAS), ranging from 1 to 10. One indicates no pain, and 10 indicates the worst pain one could image.

Secondary Outcome Measures

1. Pain scores at 12 hours, 48 hours, and 72 hours post-operatively.
2. Morphine milligram equivalences consumed during hospital stay

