3. Morphine milligram equivalences prescribed and consumed as measured at one week follow up clinic visit
4. Post-operative nausea and vomiting (PONV) measured by a numerical score (1: no nausea or vomiting, 2: some nausea no vomiting, 3: nausea and vomiting)
5. Length of stay in hours
6. Patient satisfaction score

These parameters will be scored via SeamlessMD on a phone application, as well as paper and pen on a standardized reporting form for patients less comfortable using technology. Data will also be collected from patient electronic charts.

Analytical Plan

Equivalency test with priori specified non-inferiority region will be used to assess primary outcome variables.

Descriptive statistics (mean, range, percentage, median, etc.) will be used to assess the quality and accuracy of the administrative and clinical data. Means with standard deviations or medians with interquartile range (IQR) will be reported for continuous variables and percentages for categorical variables. Missing data will be evaluated prior to data modeling. General linear regression, or other generalized linear regression models will be used to compare the outcomes between the two groups with both univariate or multivariate analyses. Potential confounders will be identified with univariate analysis. For univariate analyses, a Student's t-test or Wilcoxon two-sample test will be used for continuous variables, and chi-square test for categorical variables against the primary and secondary outcomes. Both unadjusted and adjusted odds ratio (OR) with

corresponding 95% confidence interval (CI) will be reported. Two-tailed p values will be calculated for all tests, and $p < 0.05$ is considered statistically significant. All data will be analyzed using Statistical Analysis Software, version 9.4 (SAS Institute Inc., Cary, NC).

There are no plans for interim data analyses. Analyses will be conducted according to per-protocol (PP) principle.

Human Subjects Protection

Subject Recruitment Methods

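### Exclusion 2 is not limited to planned procedures, so a randomised patient already given the block may be removed by someone who may know the arm, and no all-randomised analysis would show the effect.

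*Combined protocol and SAP*

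**What the plan says.** Five parts of the combined protocol and SAP bear on this point.

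- **Exclusion Criteria, item 2** excludes "Patients undergoing concomitant hiatal hernia repair or ventral hernia repair or cholecystectomy at time of primary metabolic surgery". It does not say whether this means procedures planned in advance or also those decided on during the operation.
- **Interventions and Interactions** fixes the timing of treatment: "TAP block will be administered at the start of every case, after the first port is placed upon laparoscopy". The technique is described as "using laparoscopic-guided approach", but the person giving the block is not named. The Background says "The TAP block can also be performed by the surgeon with laparoscopic guidance", which is a general remark and not a trial instruction.
- **Interventions and Interactions** also says "Eligible patients will be randomized with a 1:1 ratio between the 2 groups". When randomisation happens relative to surgery is not stated. Under Subject Recruitment Methods, patients are recruited at the preoperative clinic visit on the basis of the scheduled operation.
- **Design** calls the trial single blinded and adds "Patients will be blinded to type of TAP block used". No one else is named as blinded.
- **Analytical Plan** says "Analyses will be conducted according to per-protocol (PP) principle". The per-protocol set is not defined, and there is no intention-to-treat or modified intention-to-treat analysis.

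The Sample Size section allows 20% for dropout or withdrawal. It does not mention removals for a concomitant procedure.

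**The concern.** Read together, these sections leave open a route by which patients can leave the trial after treatment. The block is given just after the first port. Any hernia repair or cholecystectomy decided on later in the operation follows both allocation and treatment. If exclusion 2 is then applied, a treated patient becomes ineligible, and under the usual meaning of per-protocol that patient leaves the analysis.

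Two things would be at stake. The first is the comparison itself. If the decision to operate further, or to classify the patient as excluded, were related to arm, the two analysed groups would no longer be the groups that randomisation formed. With no analysis of all randomised patients, a reader of the results could not see this. The second is precision: such removals may come on top of the loss already allowed for.

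**Working it through.** **Inputs from the Sample Size section:** SD 3 per group, margin 1.5, true difference 0, alpha 0.05, 88 per group for 90% power, 20% dropout or withdrawal, 106 per group. The sidedness of alpha is not stated.

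**Step 1: reproduce the plan's figure.** Two one-sided t-tests at 0.05 each, with limits of ±1.5:

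- SE = 3 × √(2/88) = 0.452, so margin/SE = 1.5/0.452 = 3.32.
- Normal approximation: power = 2 × Φ(3.317 − 1.645) − 1 = 0.905.
- Integrating over the distribution of the pooled variance (the t-based calculation) gives 0.903, and 88 is the smallest n per group that reaches 0.90.

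The stated 88 reproduces with alpha read as 0.05 per one-sided test.

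**Step 2: set aside the inflation error.** 88 × 1.20 = 105.6, rounded up to 106. After a 20% loss, 106 × 0.80 = 84.8, so 84 complete patients per group and power 0.886. Keeping 88 would need 88/0.80 = 110. The fall from 90% to 88.6% is therefore already in the plan and is not part of this point.

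**Step 3: add removals under exclusion 2.** The documents give no rate of unplanned concomitant procedures, so the rates x below are assumptions. They are taken to be additional to the 20%. Evaluable n per group = 106 × 0.80 × (1 − x), rounded down. The number to randomise per group to keep 88 evaluable = 88 / (0.80 × (1 − x)), rounded up.

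| Assumed extra loss x | Evaluable per group | Power | Randomised per group to keep 88 |
|---|---|---|---|
| 0 | 84 | 0.886 | 110 |
| 5% | 80 | 0.867 | 116 |
| 10% | 76 | 0.845 | 123 |
| 15% | 72 | 0.820 | 130 |
| 20% | 67 | 0.783 | 138 |

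Measured from 88.6%, the loss is about 2 points at 5%, 4 at 10%, 7 at 15% and 10 at 20%.

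**Step 4: illustrate selective removal.** Suppose a fraction q of one arm only is removed, and those patients' mean pain score differs by D points from the rest of that arm. The estimated difference then shifts by q × D. With q from 5% to 15% and D from 1 to 3, both assumed, the shift runs from 0.05 × 1 = 0.05 to 0.15 × 3 = 0.45 points. Take 84 per group, a true difference exactly at 1.5, and a shift towards zero. The chance of wrongly declaring equivalence rises from 0.05 to between about 0.06 and 0.25. This shows how sensitive the test would be; it is not evidence that such selection would occur.

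**The case against.** The strongest reply is that exclusion 2 is a pre-enrolment criterion. Eligible patients are the ones randomised, recruitment is from scheduled operations, and inclusion 3 and exclusion 1 use the word undergoing for planned surgery. On this reading, the reference to the time of surgery only explains what concomitant means. That reading is fair and may be what the sponsor intends. It does not settle the matter, because the text does not say so and does not say what happens to a randomised patient with an unplanned procedure.

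A reader might infer three stronger things that the documents do not support.

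- *The operator knows the arm.* The single-blind wording permits this, but the documents do not say who prepares or gives the block, or who sees the allocation.
- *The per-protocol rule removes these patients.* The set is undefined, so removal is a likely reading and not a stated rule.
- *The randomised comparison is broken.* Nothing in the documents links the anaesthetic mixture to a decision to repair a hernia or remove a gallbladder, and a condition present before the block cannot be caused by it. If the decision does not depend on arm, these removals cost patients without biasing the comparison.

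It is also fair that per-protocol analysis is common in equivalence trials. It is normally prespecified in detail and accompanied by an analysis of all randomised patients, and here it is neither. Finally, the 20% allowance might already include some such removals, since the text does not say. The power losses in the table are therefore conditional on the removals being additional.

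**Conclusion.** The gap is real but conditional. The protocol does not limit exclusion 2 to planned procedures, does not define the per-protocol set, names only patients as blinded, and has no all-randomised analysis. Removal of treated patients by someone aware of the arm is therefore possible and would go unseen. The documents do not show that it would happen, how often, or in which direction.

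On the plan's own SD and margin, the cost in power is modest unless such procedures are frequent: only the assumed 20% rate takes power below 80%. The possible effect on validity matters more but cannot be sized from the documents. The change is worth making because it is cheap and closes a route to selection after treatment. Confidence is medium: the gap is plain in the text, but its frequency is unknown.

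**What to change.** 1. Reword exclusion 2 so that it applies only to concomitant procedures planned before randomisation.
2. Add an analysis of all randomised patients who received a block, by allocated arm, alongside the per-protocol analysis.
3. Define the reasons for leaving the per-protocol set in advance, apply them blind to arm, and report removals by arm and reason.
4. Add a sensitivity analysis without the patients who had an unplanned concomitant procedure.

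Holding back the allocation until after the first look through the first port is a tempting alternative. It would not cover procedures decided on later in the case, so it is not recommended.

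The cost is protocol wording, a little more analysis work, and slightly more variable pain scores from patients with added procedures. That variability would offset some of the power regained by keeping them; the documents give no figure for how much.

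### The 20% dropout allowance was multiplied on (88 × 1.2 = 106) when it should be divided out (88 / 0.80 = 110), so 106 per group leaves about 85 evaluable, not 88

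*Combined protocol and SAP*

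**What the plan says.** The Sample Size section gives these assumptions: "we assume standard deviation for each group is 3", "the margin of equivalence is 1.5 on NRS", and a true difference of 0. It concludes: "Group sample size of 88 from each group achieves 90% power to detect our prespecified equivalence margins, with alpha of 0.05". The allowance for losses follows at once: "Assuming a 20% dropout or withdrawal based upon previous experience, 106 subjects per group will be required". No inflation formula is given.

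The Analytical Plan bears on whether lost patients could be recovered. On missing data it says only: "Missing data will be evaluated prior to data modeling". On the analysis set it says: "Analyses will be conducted according to per-protocol (PP) principle".

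On the type of test the document is mixed. The Design section says: "This study is a 2-arm parallel single blinded randomized equivalency, single-center, clinical trial". The Primary Hypothesis, however, is written in one direction only, and says that δ "is non-inferiority margin, specified in advance based on clinical judgement".

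**The concern.** The power calculation sets a target of 88 patients per group in the analysis. The enrolment figure should be large enough for 88 to remain after the assumed loss. A loss of 20% is a share of those enrolled, so the target has to be divided by 0.80. The stated 106 looks like the target increased by 20%, which falls short.

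If so, the plan's enrolment, dropout rate, evaluable number and power cannot all be true together. This paragraph is the trial's only justification of its size, and a reader can see the inconsistency by taking 80% of 106.

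**Working it through.** **Inputs (Sample Size section unless noted).** SD 3 in each group; margin δ = 1.5; true difference 0; alpha 0.05, sidedness not stated there; 88 per group for 90% power; dropout 20%; 106 enrolled per group. Allocation is 1:1 (Interventions and Interactions).

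**Step 1: reproduce 88.** With n per group, SE = SD × √(2/n). Under TOST with true difference 0, approximate power is 2Φ(δ/SE − z₀.₉₅) − 1, where z₀.₉₅ = 1.645.

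- Solving for 90% power: n = 2 × (3 × (1.645 + 1.645) / 1.5)² = 86.6, so 87 by the normal approximation.
- The exact calculation replaces z by the t quantile on 2n − 2 degrees of freedom and integrates over the distribution of the pooled variance. It gives 89.9% at 87 and 90.3% at 88, so 88 is the smallest n that reaches 90%.

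Other readings do not give 88:

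| Test | Result (exact) |
|---|---|
| TOST, 5% per side | 88 per group (90.3%) |
| One-sided non-inferiority, alpha 0.05 | 70 per group (90.3%) |
| One-sided non-inferiority, alpha 0.025 | 86 per group (90.3%) |

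TOST at 2.5% per side gives only 82.5% power at 88 (normal approximation). The plan's 88 is therefore matched by TOST at 5% per side.

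**Step 2: the dropout allowance.**

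- Multiplying: 88 × 1.20 = 105.6, rounded up to 106. This is the stated figure.
- Dividing: 88 / (1 − 0.20) = 110.
- Evaluable from 106: 106 × 0.80 = 84.8, against 88 needed.
- Evaluable from 110: 110 × 0.80 = 88.
- Largest loss at which 106 still leaves 88: 1 − 88/106 = 17.0%.

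The shortfall is 88 − 84.8 = 3.2 evaluable per group, or 110 − 106 = 4 enrolled per group (2 × 106 = 212 against 2 × 110 = 220 in total). None of this depends on the test.

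**Step 3: effect on power under TOST at 5% per side (exact).**

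| Evaluable per group | Power |
|---|---|
| 84 | 88.6% |
| 85 | 89.1% |
| 87 | 89.9% |
| 88 | 90.3% |

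If the number evaluable in each group is random, Binomial(N, 0.80), expected power is 88.9% from N = 106 and 90.2% from N = 110.

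**Step 4: how this compares with uncertainty in the SD.** At 85 per group, an SD of 2.95 gives 90.2% and an SD of 3.05 gives 87.8%. A shift of 0.05 in the SD moves power by about as much as the dropout error.

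**The case against.** The arithmetic is not in dispute. The case against concerns weight and certainty.

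- **The effect is close to nil.** About one point of power is less than the uncertainty in an SD taken from clinical experience. The 20% is a round figure, and 106 would suffice if the loss were 17%. This stands, and is why the point is minor. The sentence nevertheless says 20%.
- **The power loss depends on the test.** The only formal primary hypothesis is one-sided, with δ called a non-inferiority margin. Tested that way, 85 per group gives 94.5% power at alpha 0.05 or 90.0% at alpha 0.025, so there is no meaningful shortfall. This stands as a condition on the power figure. TOST remains the better reading of the sample-size paragraph, because it alone among the variants tried gives 88 and it matches the equivalence design. The document never names it, however.
- **Some losses may not matter at 24 hours.** The plan does not say whether the 20% is loss by the 24-hour primary assessment or over follow-up to the one-week visit, and scores might be recovered from electronic charts. This is possible but not planned. The 20% is applied directly to the primary power calculation, and per-protocol exclusions could also add to the losses.
- **The author may have meant 20% over-enrolment.** The sentence speaks of dropout or withdrawal, so it would need correcting on that reading too.

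**Conclusion.** The sentence is wrong as written. At the plan's own 20% dropout, 106 per group leaves about 85 evaluable rather than 88, and the enrolment consistent with 88 is 110. That part follows from the plan's figures alone and is firm.

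The consequence for power, about 89% rather than 90%, rests on TOST at 5% per side with SD 3, margin 1.5 and true difference 0, and on the 20% being lost from the primary analysis without replacement or imputation. The error is minor: the trial is not materially underpowered because of it, and the choice of SD matters more.

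**What to change.** Keep 106 per group and correct the sentence, for example: *With 106 enrolled per group and 20% dropout, about 85 per group are expected to be evaluable, giving about 89% power (TOST, 5% per side); 110 per group would be needed to retain 88.* The evaluable-number part can go in at once. The power part should be entered when the plan names its primary test, since the Primary Hypothesis is at present one-sided and the Sample Size section does not say how alpha is applied.

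This costs nothing beyond stating power about one percentage point lower, and it changes nothing in the conduct of the trial. If the sponsor prefers to hold 88 evaluable and 90% power at 20% dropout, enrolment becomes 110 per group, which is 8 more patients in total (220 against 212). Keeping 106 with an allowance of about 17% would also be consistent, but only if the sponsor's previous experience supports that lower rate.

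### Hypothesis 2.1 gives its opioid endpoint two different windows with no rule for choosing, and the only matching listed outcome stops at discharge, so a difference in length of stay can pass for a difference in opioid use

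*Combined protocol and SAP*

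**What the plan says.** All references are to the combined protocol and SAP.

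- **Secondary Hypotheses, 2.1:** the liposomal arm is expected to show "less opioid consumption before hospital discharge /during the first 48 hours postoperatively as measured in morphine equivalents (mg"). The slash joins two windows. Nothing says which one governs, or what happens when discharge falls before or after 48 hours.
- **Secondary Outcome Measures, item 2:** "Morphine milligram equivalences consumed during hospital stay". This is the only listed outcome that corresponds to Hypothesis 2.1.
- **Item 3:** "Morphine milligram equivalences prescribed and consumed as measured at one week follow up clinic visit". This is a separate outcome. The exploratory objectives describe a similar quantity as "total opioid consumption required post op during their one-week post op visit as measured in morphine equivalences".
- **Item 5:** "Length of stay in hours".
- **Design:** "Patients will be blinded to type of TAP block used". No other blinding is described.
- **Analytical Plan:** "General linear regression, or other generalized linear regression models will be used to compare the outcomes between the two groups", and "Two-tailed p values will be calculated for all tests". It sets no opioid window, no rule for unequal stay, and no rule for doses taken between discharge and 48 hours.

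**The concern.** Two problems compound each other.

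First, the endpoint is not defined. With two windows in the hypothesis, only one of them in the outcome list, and no choice made in the analytical plan, the window could be settled after the data are seen.

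Second, a cumulative total that stops at discharge has a follow-up time that varies by patient and is decided after randomization. Length of stay is listed as an outcome, so the plan itself allows that treatment may change it. If one arm goes home earlier, its in-hospital total is lower even when its use, hour by hour, is the same.

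Hypotheses 1.1 and 2.2 both claim equivalence of pain scores. Hypothesis 2.1 is the only numbered hypothesis that claims an advantage for the liposomal mixture. If pain proves equivalent, it is the numbered claim left to distinguish the arms.

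**Working it through.** **The plan's own figure.** The only sample-size figure is for the primary pain score: 88 per group, SD 3, margin 1.5, true difference 0, 90% power, alpha 0.05. For two one-sided tests, n = 2 × [SD × (z₀.₉₅ + z₀.₉₅) / margin]² = 2 × [3 × (1.645 + 1.645) / 1.5]² = 2 × 6.58² = 86.6, so 87. The t-based power at 88 is 90.3%. The figure reproduces. No figure is given for the opioid endpoint, and only the 88 per group is carried forward.

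**The windows side by side.**

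| Source | Window | Doses at home before 48 h |
|---|---|---|
| Hypothesis 2.1, before the slash | to discharge | excluded |
| Hypothesis 2.1, after the slash | 0-48 h | not stated |
| Outcome item 2 | to discharge | excluded |
| Outcome item 3 | measured at one week | consumption recorded, but not stated by date |

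The first and third rows agree. The second has no counterpart in the outcome list.

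**Size of the distortion in the mean.** Assumptions, none from the documents: stay of 36 h in one arm and 36 − d in the other, with identical use at every hour.

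- Constant use: apparent reduction = d/36. For d = 4, 6, 8 h this is 11%, 17%, 22%.
- Declining use with a 24 h time constant: cumulative use to time t is proportional to 1 − exp(−t/24). At 36, 32, 30 and 28 h this is 0.777, 0.736, 0.714 and 0.689. The reductions are 1 − 0.736/0.777 = 5%, then 8% and 11%.

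**Chance of a falsely significant result.** Simulation of 4,000 trials per scenario: 88 per arm; stay normal with SD 10 h, clipped to 12-96 h; lognormal between-patient use with coefficient of variation (CV) 0.5 or 0.8; two-sided t-test at 0.05 on the in-hospital total.

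| Use over time | CV | 4 h shorter | 6 h shorter | 8 h shorter |
|---|---|---|---|---|
| Constant | 0.5 | 25% | 51% | 76% |
| Constant | 0.8 | 15% | 28% | 45% |
| Declining | 0.5 | 10% | 21% | 35% |
| Declining | 0.8 | 7% | 11% | 18% |

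Nearly all of these results favour the arm discharged earlier. With equal stays the rate is about 5%.

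**The 48-hour window under the same assumptions.** If all home doses are captured, the rate is about 5% throughout. If only half of home use is reported, it is about 5-9%, 6-14% and 8-21% for 4, 6 and 8 h.

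**Other assumptions.** With stay SD 8 h, gamma-distributed use, CV 0.5 to 1.0, and use either constant or falling by day (1, 0.5, 0.25), a stay 6 h shorter gives a significant result favouring the earlier-discharged arm in 11% to 54% of trials. The order of magnitude does not hang on one set of choices.

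**The case against.** **Randomization equalises expected stay unless treatment or discharge decisions change it.** This stands. The documents give no reason to expect 4, 6 or 8 h in particular, and with equal stays there is no bias. But stay is decided after randomization, so randomization does not protect the endpoint if the arms do differ.

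**A difference in stay would usually be seen.** With SD 10 and 88 per arm, the standard error of the difference is 10 × √(2/88) = 1.51 h. A t-test detects 4, 6 or 8 h in about 75%, 98% and over 99% of trials. Where the opioid result is falsely significant, the stay difference is also significant in about 82-92% of trials at 4 h and over 99% at 6-8 h. A careful reader would be warned, but could not recover the opioid effect from the two results.

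**Several stronger readings are tempting and are not supported.**

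- A reader might count three conflicting windows. There are two: item 2 and the discharge half of Hypothesis 2.1 end at the same point.
- A reader might infer that unblinded staff decide discharge. The documents state only that patients are blinded. They do not say who decides discharge or what those staff know.
- A reader might conclude that home opioid use goes unrecorded. It is missing from item 2, but item 3 collects consumption at one week. The patient survey is listed in the appendix without its content, so whether it already dates home doses cannot be judged.
- A reader might assume that the bias favours liposomal bupivacaine. A longer stay in that arm would instead hide a real reduction.

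**A 48-hour window is not a perfect remedy.** This also stands: it depends on capture of home doses, as the half-reporting figures show.

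**Conclusion.** The point holds as a defect of a secondary endpoint that should be corrected. Confidence is high on the wording: Hypothesis 2.1 contains two windows, no rule chooses between them, and no listed outcome is a 48-hour total. Confidence is moderate on the bias. The mechanism follows from the definition of the outcome, but its size and direction depend on a between-arm difference in stay that the documents do not give. The rates of about 7-25%, 11-51% and 18-76% are illustrations under the stated assumptions, not predictions. The lowest is close to the nominal 5%. The primary pain comparison and its sample size are not affected.

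**What to change.** 1. Define the Hypothesis 2.1 endpoint once: total MME consumed from end of surgery to 48 hours, whether or not the patient has been discharged, using chart doses in hospital and patient-reported doses at home.
2. If home doses cannot be dated, use MME consumed, not prescribed, from surgery to the one-week visit, combining item 2 with the consumed part of item 3.
3. Make the outcome list and the analytical plan state the same window.
4. Keep the in-hospital total as a descriptive result, shown beside length of stay.

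A 0-24 h total next to the 24-hour pain score would help interpretation, but it is optional and not needed to repair this defect.

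The cost is a wording change and possibly one dated opioid item in the existing patient survey. The downside is recall error and incomplete reporting of home doses, so completeness should be reported by arm. Sample size and treatment do not change.
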